## **9. RESEARCH DESIGN AND METHODS**

**Overall Study Design.** The clinical trial will be registered under [www.clinicaltrials.gov](http://www.clinicaltrials.gov). Subjects between the ages of 18-65 who have a POTS diagnosis will be enrolled. Specifically, we will enroll patients who have hyperadrenergic POTS as confirmed by norepinephrine (NE) levels > 600 pg/ml. This is a 3-month study with a randomized double-blind placebo controlled cross over design. Subjects will be randomized into one of two groups (Ivabradine or placebo for one-month) then crossed over after a one-week washout period to the other group for one-month. Refer to Figure 1 below for details.

[figure not shown]

Figure 1. Randomized double-blind placebo-parallel group crossover trial with Ivabradine for patients with POTS.

**Study Visits.** There will be seven visits at the ACTRI and UCSD Cardiology clinics.

-Visit 1 is the pre-screening visit during which norepinephrine (NE) blood results will be obtained to confirm hyperadrenergic POTS diagnosis (NE> 600pg/ml). Orthostatic heart rate will be monitored. A urine pregnancy test will also be administered at this time. Post-menopausal women and women who are infertile will not be asked to take pregnancy test per PI discretion.

-At Visit 2, baseline lab work will be obtained to assess cardiometabolic health (CBC, CMP, TSH, T4, BNP). A tilt table test will be performed to determine baseline heart rate and QOL questionnaire (ShortForm36, SF36) will be completed. Orthostatic heart rate will be monitored. At this point, the patient will be randomized into the Ivabradine or placebo group for one month.

-At Visit 3, two-weeks into treatment, the patient will return to ACTRI for drug titration. Orthostatic heart rate will be monitored. If the patient fulfills criteria (see **Ivabradine Dosing** below), they will either increase, decrease, stop, or not change their Ivabradine dose.

-At Visit 4, one month after starting the current treatment, orthostatic heart rate monitoring, NE bloodwork, and QOL questionnaires will be completed. There will be a one-week wash-out period before the patient crosses over to the other group for one month.

-At Visit 5, the patient will return for orthostatic heart rate monitoring, NE bloodwork, and QOL questionnaires. A urine pregnancy test will be administered at this time. Post-menopausal women and women

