who are infertile will not be asked to take pregnancy test per PI discretion. The patient will be instructed to begin the secondary treatment (placebo or Ivabradine) for one month.

-At Visit 6, two-weeks into this treatment, the patient will return to ACTRI for drug titration. Orthostatic heart rate will be monitored. If the patient fulfills criteria (see **Ivabradine Dosing** below), they will either increase, decrease, stop, or not change their Ivabradine dose.

-At Visit 7, one month after starting the secondary treatment, the patient will return for orthostatic heart rate monitoring, NE bloodwork, and QOL questionnaires.

Blood samples will be saved and securely stored with the PI for future research analysis and purposes.

**Randomization.** Randomization refers to the order in which patients receive placebo or Ivabradine. If a patient receives Ivabradine first for one month, then he/she will be switched over to placebo for one month. If a patient receives placebo first for one month, then he/she will be switched over to Ivabradine for one month. There will be a one-week washout period prior to the cross-over. There will be 10 patients in each group.

**Ivabradine Dosing.** Ivabradine dose will initiate at 5mg twice daily (bid) and be increased to 7.5mg twice daily (bid) after 2 weeks if the heart rate is greater than 70 beats/min. If the heart rate is less than 70 beats/min there will no increase in dose. If the heart rate is less than 50 beats/min, or if the patient has symptoms of dizziness or lightheadedness, then Ivabradine will be stopped.

If patients have side effects and feel that cannot continue with Ivabradine we will decrease the dose from 7.5mg bid to 5mg bid (or if they are on 5mg bid to 2.5mg bid). After this dose reduction if the patient is still unable to tolerate Ivabradine, we will stop Ivabradine and withdraw patient from the study. If a patient is unable to tolerate Ivabradine (particularly prior to crossover period), he/she will be withdrawn. The starting dose and titration model is the same for the crossover treatment period as the initial month.

In our clinical experience using Ivabradine in patients with inappropriate sinus tachycardia (which are very similar to POTS patients in age and co-morbidities) we have not seen significant side effects that have caused patients to stop the drug. Refer to the uploaded Ivabradine Drug Information document for more details.

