- k. Woman of childbearing potential who are unwilling to use highly effective contraception during treatment and for an additional one month after discontinuing the study drug.

Highly effective contraceptive method (methods that can achieve a failure rate of less than 1% per year when used consistently and correctly) include:

- Combined hormonal (estrogen and progestogen) contraception associated with inhibition of ovulation (oral, intravaginal, transdermal)
- Progestogen - only hormonal contraception associated with inhibition of ovulation (oral, injectable, implantable)
- Intrauterine device (IUD)
- Intrauterine hormone-releasing system (IUS)
- Bilateral tubal occlusion
- Vasectomized partner
- Sexual abstinence
- Infertility

If the patient or patient's significant other is infertile, the PI may not require the patient to start other highly effective contraceptive methods in this case as they deem appropriate. The PI shall discuss with the patient and document the decision. The research team will document this in the patient's study file.

For female participants, the PI will administer a pregnancy test at the first visit to determine if patient will be excluded. Another pregnancy test will be administered prior to starting the crossover treatment.

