## 11. RECRUITMENT

We aim for 20 adult volunteers with confirmed hyperadrenergic POTS (NE > 600pg/ml) to complete the study. We will screen at least 60 patients in order to have 20 pass the screening phase and complete the study. With an expected drop-out of 10% after enrollment, this will provide 18 subjects for final analysis, which provides adequate power to detect a significant improvement in decreasing average heart rate at the 0.05 level (see power analysis, above). Participants will be screened and must meet inclusion and exclusion criteria before they are enrolled into the study. Additionally, the PI may ask a patient to return for a reevaluation of the baseline screening norepinephrine levels with a blood draw if she has reason to believe that the blood draw was done incorrectly or the results are inaccurate. This would be an additional in-person visit, but it does not increase the risk of the study.

We will recruit from the UCSD Medical Center cardiology and internal medicine clinics. Also, we will be utilizing ResearchMatch and the bioinformatics report from EPIC to help recruit patients who may qualify for our inclusion criteria. Each of these patients will be randomized into one of the two groups mentioned (Ivabradine or placebo).

We will be screening and recruiting patients through UCSD Medical Center clinics. We will also use ResearchMatch, which enables researchers to search for appropriate matches in non-identifiable volunteer profiles. We will be screening patients through EPIC, with the help of their bioinformatics department, for research subjects who might qualify for our criteria. EPIC Bioinformatics will help search for the following to generate a list of potential research subjects:

1. Patient's name, date of birth (DOB), and Medical Record Number (MRN)
2. Patient's primary care provider (PCP) name and contact information
3. POTS diagnosis
4. NE levels >600pg/dl
5. Ages 18-65
6. Exclusion:
  - a. History of thyroid disease requiring dose titration of thyroid replacement medication(s) within the past 3 months (i.e. hypothyroidism on a stable dose of thyroid replacement therapy is not an exclusion)
  - b. Drugs that interfere with Ivabradine (example: Cytochrome P450 drugs)
  - c. Presentation of peripheral edema and discolored toes with peripheral autonomic neuropathy. Symptoms include: legs (reduced hair growth, cramps), toes (blue color), legs/feet (wounds, ulcers that do not heal), and muscles (numbness, heaviness)

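### No pregnancy test is scheduled at Visit 2, so patients who receive ivabradine first are not retested when active drug starts

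*Combined protocol and SAP*

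**What the plan says.** Two sections of the protocol deal with pregnancy testing, and they agree.

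- **Section 10, Human Subjects**, after the contraception list: "the PI will administer a pregnancy test at the first visit to determine if patient will be excluded". It then adds: "Another pregnancy test will be administered prior to starting the crossover treatment".
- **Section 9, Study Visits.** "Visit 1 is the pre-screening visit during which norepinephrine (NE) blood results will be obtained", and a urine pregnancy test is done at that visit. At Visit 2 the listed procedures are CBC, CMP, TSH, T4, BNP, a tilt table test, the SF-36 and orthostatic heart rate. Then: "At this point, the patient will be randomized into the Ivabradine or placebo group for one month". Visit 5 includes the second test ("A urine pregnancy test will be administered at this time"), and at that same visit "The patient will be instructed to begin the secondary treatment (placebo or Ivabradine) for one month".

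Post-menopausal and infertile women may be exempted from testing. Pregnancy is an exclusion (section 10, j). Exclusion k removes women of childbearing potential who are "unwilling to use highly effective contraception during treatment and for an additional one month after discontinuing the study drug". The safety monitoring plan in section 15 provides for stopping the drug if a pregnancy occurs.

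**The concern.** The plan tests at the visit where the second treatment period begins but not at the visit where the first begins. For the first period it relies on the pre-screening result, which is older by however long it takes to get from Visit 1 to Visit 2. The plan puts no limit on that time.

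The effect differs by sequence. Patients who take placebo first are tested at the visit where they start ivabradine. Patients who take ivabradine first are not.

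At stake is avoidable exposure of a pregnancy to the study drug. A woman in the ivabradine-first sequence who conceives between Visits 1 and 2 could take the full month of ivabradine and complete the washout before the next scheduled test. Weekly follow-up includes no pregnancy test, and the discontinuation rule acts only once a pregnancy is known, which is after exposure. A test at Visit 2 would act before exposure, and before one of 20 randomised places is used.

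**Working it through.** The plan gives no figure on this point to reproduce. The check is a reading of the schedule followed by a rough sizing.

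**1. Schedule, from sections 9 and 10**

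| Visit | Role | Pregnancy test |
|---|---|---|
| 1 | Pre-screening, norepinephrine | Yes |
| 2 | Baseline and randomisation to period 1 | No |
| 3 | Two weeks into period 1 | No |
| 4 | End of period 1 | No |
| 5 | After washout, start of period 2 | Yes |
| 6 | Two weeks into period 2 | No |
| 7 | End of period 2 | No |

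**2. By sequence (10 patients planned in each)**

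- Placebo first: ivabradine starts from Visit 5, and a test is done at Visit 5.
- Ivabradine first: ivabradine starts from Visit 2, and the last test was at Visit 1. The Visit 5 test comes before placebo.

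**3. What can separate Visits 1 and 2**

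The norepinephrine result decides eligibility. Section 11 also allows for delay: "the PI may ask a patient to return for a reevaluation of the baseline screening norepinephrine levels with a blood draw", which is an additional in-person visit. Section 9 (Assessments) requires a one-week washout for patients on midodrine, Florinef or ivabradine. It does not say whether that falls before or after Visit 1, so the washout may or may not add to the gap.

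The length of the gap is not stated. If the 3-month study length in section 9 includes screening, with 3 months taken as 13.0 weeks, the time left before Visit 2 is:

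- calendar months: 13.0 − (2 × 4.35 + 1) = 3.3 weeks
- four-week months: 13.0 − (2 × 4 + 1) = 4.0 weeks

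Because the 3-month figure is rounded, a range of 1 to 4 weeks is assumed.

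**4. Number of women**

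The only sex ratio in the document is the 5:1 background ratio in section 5. Applying it to enrolment is an assumption.

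- Whole trial: 20 × 5/6 = 16.7
- Ivabradine-first: 10 × 5/6 = 8.3

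**5. Chance of any conception in the gap, ivabradine-first group**

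Section 10 defines highly effective contraception as a failure rate below 1% per year. Taking that ceiling, and treating all 8.33 women as fertile, with w the gap in weeks:

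P = 1 − 0.99^(8.33 × w/52)

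| w (weeks) | P |
|---|---|
| 1 | 0.16% |
| 2 | 0.32% |
| 3 | 0.48% |
| 4 | 0.64% |

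These are probabilities for the group as a whole, not per woman. They count any conception in the gap, and a Visit 2 urine test would not necessarily detect all of them. The documents give no detection lag, so the exposure actually averted cannot be calculated.

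**The case against.** The strongest reply is that the plan already screens every non-exempt woman before her first dose, so what is missing is recency and not the test itself. That is correct, and the point should be read that way.

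The size of the problem can also be challenged. The 0.2% to 0.6% range uses the contraceptive failure ceiling and ignores exempt women, so it is on the high side if contraception is in use throughout. The gap is assumed. The washout is tied to the baseline norepinephrine workup and tilt test, and norepinephrine is drawn at Visit 1, so the washout may well come before Visit 1 and add nothing. The repeat draw is discretionary and is itself a visit at which a test could be done. All of this stands, and it keeps the risk small.

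On contraception, it is fair to say that exclusion k is judged at screening and that most of the listed methods would already be in place by the first dose. Even so, the wording covers treatment and the month afterwards, and does not expressly cover the interval before treatment. If some women began contraception only with treatment, the risk would be higher, and the documents give no rate for that case. The plan also retests at Visit 5 although contraception is required throughout period 1, so it does not treat contraception as a substitute for a test.

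The consent form, the drug information document and Figure 1 were not available and might contain further precautions. The two sections that can be read agree in omitting a Visit 2 test.

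**Conclusion.** The concern holds. Pregnancy status is not rechecked when first-period treatment starts, and the interval since the Visit 1 test has no upper limit. The 10 ivabradine-first patients therefore begin active drug on a pre-screening result, whereas the 10 placebo-first patients are retested at the visit where they begin it. The plan gives no reason for the difference.

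The absolute risk is low: roughly 0.2% to 0.6% for any conception in the gap among ivabradine-first patients. That range rests on the assumed 5:1 ratio, full fertility, the 1% per year ceiling and a gap of 1 to 4 weeks. The schedule facts are certain and the size is not. The estimand, sample size, power and analysis are unaffected. The change is worth making because it is cheap and applies the plan's own Visit 5 practice to period 1.

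**What to change.** Add a urine pregnancy test to the Visit 2 procedures in section 9, done before randomisation and dispensing, with the same exemptions as at Visits 1 and 5. Amend the testing statement in section 10 to name all three time points.

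The cost is one urine test per non-exempt woman at an existing visit: at most about 17 tests (20 × 5/6 = 16.7) if the 5:1 ratio applies. No new visit or type of procedure is needed.

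A short maximum interval between Visits 1 and 2, with a retest only when it is exceeded, would also address the point. The Visit 2 test is simpler to run and matches what is already done at Visit 5.

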## 11. RECRUITMENT

We aim for 20 adult volunteers with confirmed hyperadrenergic POTS (NE > 600pg/ml) to complete the study. We will screen at least 60 patients in order to have 20 pass the screening phase and complete the study. With an expected drop-out of 10% after enrollment, this will provide 18 subjects for final analysis, which provides adequate power to detect a significant improvement in decreasing average heart rate at the 0.05 level (see power analysis, above). Participants will be screened and must meet inclusion and exclusion criteria before they are enrolled into the study. Additionally, the PI may ask a patient to return for a reevaluation of the baseline screening norepinephrine levels with a blood draw if she has reason to believe that the blood draw was done incorrectly or the results are inaccurate. This would be an additional in-person visit, but it does not increase the risk of the study.

We will recruit from the UCSD Medical Center cardiology and internal medicine clinics. Also, we will be utilizing ResearchMatch and the bioinformatics report from EPIC to help recruit patients who may qualify for our inclusion criteria. Each of these patients will be randomized into one of the two groups mentioned (Ivabradine or placebo).

We will be screening and recruiting patients through UCSD Medical Center clinics. We will also use ResearchMatch, which enables researchers to search for appropriate matches in non-identifiable volunteer profiles. We will be screening patients through EPIC, with the help of their bioinformatics department, for research subjects who might qualify for our criteria. EPIC Bioinformatics will help search for the following to generate a list of potential research subjects:

1. Patient's name, date of birth (DOB), and Medical Record Number (MRN)
2. Patient's primary care provider (PCP) name and contact information
3. POTS diagnosis
4. NE levels >600pg/dl
5. Ages 18-65
6. Exclusion:
  - a. History of thyroid disease requiring dose titration of thyroid replacement medication(s) within the past 3 months (i.e. hypothyroidism on a stable dose of thyroid replacement therapy is not an exclusion)
  - b. Drugs that interfere with Ivabradine (example: Cytochrome P450 drugs)
  - c. Presentation of peripheral edema and discolored toes with peripheral autonomic neuropathy. Symptoms include: legs (reduced hair growth, cramps), toes (blue color), legs/feet (wounds, ulcers that do not heal), and muscles (numbness, heaviness)
  - d. Subjects who have had a history of systemic illnesses (acute or chronic infectious); active and/or uncontrolled autoimmune/inflammatory disease, COPD, anemia, or diabetes.
  - e. History of malignancy undergoing active treatment, except non-melanoma skin cancer.
  - f. Uncontrolled psychiatric disorder (including history of hospitalization for psychiatric illness).
  - g. Subjects with resting heart rate <60beats/min, atrial fibrillation, advanced AV blocks, sinus disease, and acute decompensated heart failure and severe hepatic impairment.
  - h. Smokers or alcohol abuse
  - i. Pregnant women or breastfeeding mothers
  - j. Woman of childbearing potential who are unwilling to use highly effective contraception during treatment and for an additional one month after discontinuing the study drug

After we identify patients of interest for the study, we will contact their primary care provider and get their approval to contact the patient. We will inform clinicians in the department of endocrinology, cardiology family medicine and internal medicine of our study. We will ask these clinicians to ask their patients if they are interested in our study. We will also ask the clinicians to specifically ask the interested patients if it is

acceptable if our research team contacts them. If the patients are interested and give their consent then our study coordinator will either contact them by phone or after their clinic visit.

We will be screening patients prior to informed consent. The following are justifications for partially waiving the HIPAA for screening purposes:

7. It allows the timely review of PHI for patients who are visiting the UCSD clinics, which will allow a greater chance of finding eligible patients. It is imperative that we consent the right patients for the study in order to:
  - a. Reduce the probability of screen failures, and minimize the waste of resources, time and funds.
  - b. Conduct research more smoothly and efficiently, without having to unnecessarily disturb patients who do not qualify for our study.
8. We will be using the partial HIPAA waiver only for the purposes of determining the eligibility of patients, and nothing more. This information can only be determined by screening the patients' medical records on Epic.
9. Screening cannot be practicably conducted without the use of PHI because subject eligibility depends on inclusion and exclusions factors that can only be found in their medical records. The PHI we will be using during the screening process are the patient's age, sex, past medical history, active problems, procedures, images, and medications. Only the PI and the research team will have access to this information.
10. There will be no disclosure of data to anyone outside this research group. PHI will be protected from improper use/disclosure. This will be done by securing the PHI in a locked cabinet in the PI's locked office at the Altman Clinical Translational Research Institute (ACTRI). Only the PI and the research team will have the keys to the office and the cabinet so that only they can review the documents. The PHI will never leave the office or the building.
11. The use of PHI by our research team does not involve more than minimal risk since there are no routine physical or psychological examinations or tests for screening.
12. The research could not be practicably conducted without the waiver since we have to screen the subject prior to recruiting them into the study.
13. The privacy risks are reasonable relative to the anticipated benefits of the research, since the results of the study may improve patient compliance in taking statins, an important drug for cardiovascular disease.
14. If the patient does not qualify, or does not agree to participate in the study, his/her PHI will not be re-used and will be destroyed at the earliest opportunity.

## **12. INFORMED CONSENT**

See attached consent.

Informed consent will be obtained by the study coordinators or research assistants associated with this protocol. Informed consent procedures will be supervised either by the study coordinator, supervising physicians, or the principal investigator. All research personnel giving informed consent will have undergone

---

proper training and obtained the required certificates.

The following are justifications for **partially waiving informed consent** for screening purposes:

1. It allows the timely review of PHI for patients who are visiting the UCSD clinics, which will allow a greater chance of finding eligible patients. It is imperative that we consent the right patients for the study in order to:
  - a. Reduce the probability of screen failures, and minimize the waste of resources, time and funds.
  - b. Conduct research more smoothly and efficiently, without having to unnecessarily disturb patients who do not qualify for our study.
2. **Minimal Risk:** The screening procedures are considered minimal risk to the potential subjects because we will be using the partial consent waiver only for the purposes of determining the eligibility of patients, and nothing more. This information can only be determined by screening the patients' medical records on Epic. Screening **cannot be practicably conducted without the use of PHI** because subject eligibility depends on inclusion and exclusions factors that can only be found in their medical records. The PHI we will be using during the screening process are the patient's age, sex, past medical history, active problems, procedures, images, and medications. Only the PI and the research team will have access to this information. There will be no disclosure of data to anyone outside this research group. PHI will be protected from improper use/disclosure. This will be done by securing the PHI in a locked cabinet in the PI's locked office at the Altman Clinical Translational Research Institute (ACTRI). Only the PI and the research team will have the keys to the office and the cabinet so that only they can review the documents. The PHI will never leave the office or the building. The use of PHI by our research team also does not involve more than minimal risk since there are no routine physical or psychological examinations or tests for screening. If the patient does not qualify, or does not agree to participate in the study, his/her PHI will not be re-used and will be destroyed at the earliest opportunity.
3. **Rights and Welfare of Subjects:** The waiver of consent would not adversely affect the rights and welfare of the potential subjects. Their standard of care in the hospital will remain the same regardless of the partial waiver of consent.
4. The potential subject will be informed about the purpose of the study, the duration of the study, the activities they will be doing in the study, the risks and benefits, expenses, compensation, alternatives to participating, privacy, their rights as research subjects and study contact information.
5. The privacy risks are reasonable relative to the anticipated benefits of the research, since the results of the study may improve patient's symptoms and be a potential treatment for POTS.

